13.4.3 Subgroup Analysis

Subgroup analysis will be performed by radiation type (HIGRT vs. SBRT) to examine potential differential effect on overall survival (OS).

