1.4.7 Rationale for Hypofractionated (HIGRT/SBRT) Dose and Fractionation (5-6.6 Gy x 5)

It is unclear whether HIGRT or SBRT is better in the neoadjuvant setting and both have been shown to be effective in sterilizing the tumor margin of primary pancreatic tumors. HIGRT is less technically demanding than SBRT and therefore can be delivered at most radiation clinics. Conversely, SBRT requires the use of motion management strategies including gating (tracking of tumor during breathing), breath hold (radiation beam is only on while the patient holds their breath at a specific position), and abdominal compression (pressure is applied to the upper abdomen to limit the range of diaphragmatic excursion and thus tumor motion) with complex radiation planning and therefore may not be able to be delivered at all radiation facilities. **Sites that enroll patients will decide whether to utilize either SBRT or HIGRT on this trial. SBRT is the recommended and preferred radiation technique for this protocol. However, if centers are not able to deliver SBRT or the patient is inappropriate for SBRT, then HIGRT will be delivered.**

At this time, there is no clear consensus regarding an optimal fractionation schedule for patients with borderline resectable or locally advanced pancreas cancer [24, 25]. To date, Stanford has treated more than 150 patients with SBRT, and this treatment has resulted in local control rates of >90% with acceptable acute GI toxicity. A single fraction of Linac-based SBRT (25 Gy x 1) has resulted in excellent tumor control. However, close to 50% of these patients developed late grade 2-5 duodenal toxicity within one year, primarily because of the proximity of the duodenum to the pancreas. Delivering hypofractionated radiation (5 or 6.6 Gy over 5 days) instead of single fraction treatment appears to result in similar tumor control with less late toxicity (<20%) [13, 26-28].

Using the linear-quadratic formulation, the biologically equivalent dose (BED) of the proposed fractionation schedules are given in comparison to other commonly used schemes (Table 1). The proposed 6.6 Gy x 5 schedule (BED early/late 54.8/105.6) closely approximates that of standard chemoradiation (BED early/late

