7.2 Radiotherapy (Arm 2 Only)

NOTE: Arm 2 closed to new patient enrollment on 08/13/2018, and further Arm 2 treatment for enrolled patients ceased as of 08/13/2018.

An optional, yet recommended, short online tutorial for radiation planning and treatment is available for review.

- Go to the EduCase website – <http://www.educase.com>
- Register on educase.com by clicking the “Login” tab, “Don’t have an account?” link, and complete the required registration information.
- Once logged in, navigate to EduCase > Case Listing. In the right-hand menu, navigate to: EduCase > Events > Alliance
- The password is “borderline”
- On the Alliance Case Listing page will be all of the links to optional video tutorials for physicians (treatment planning), dosimetry, physics, and therapists.
- There is also a practice case to review contouring of anatomy.

Patients will receive either:

- Stereotactic body radiation therapy (SBRT)
- or
- Hypofractionated image guided radiation therapy (HIGRT).

SBRT should be used for all patients (if appropriate) as it is strongly preferred. The following are required for patients to be eligible for SBRT:

- Centers delivering SBRT must be credentialed for SBRT ([Section 15.1.2](#)).
- Patients with active duodenal or gastric ulcers are not acceptable for SBRT. Patients with previous ulcers that have resolved (no active bleeding or symptoms) are acceptable for SBRT.
- Patients with direct tumor invasion of the bowel or stomach based on endoscopy are not acceptable for SBRT, but may be considered for HIGRT.
- Patients should not be treated with SBRT if SBRT-specific organ at risk (OAR) constraints cannot be met; these patients should be considered for HIGRT.
- Patients should have 4D CT simulation to assess tumor motion with respiration
- Patients should be treated with SBRT only if tumor motion can be minimized using motion management techniques, when applicable.
- SBRT requires the ability to perform daily image guidance.

HIGRT should only be considered in the following situations:

1. Centers that are not credentialed for SBRT may treat with HIGRT if appropriately credentialed ([Section 15.1.2](#)).
2. Direct tumor invasion of the bowel or stomach on endoscopy is acceptable for HIGRT.

3. Active duodenal or gastric ulcers are not acceptable for HIGRT. Patients with previous ulcers that have resolved are acceptable. This must be confirmed at the time of fiducial placement.

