- Fiducials and/or clips should be contoured separately starting superiorly and moving inferiorly in numeric order. It is often easier to delineate them in the bone window. The stent can also be contoured for reference, but the fiducials should be the primary surrogate for tumor motion and localization.
- If treating free-breathing, the fiducials should be contoured at the two extreme phases of the breathing cycle on 4D CT to outline the range of motion during breathing.
- The fiducial volumes should be expanded 3 mm to create “fiducial exp.”
- Note: If insurance does not cover fiducial placement, HIGRT only will be allowed.

Clinical Target Volume (CTV):

- Because elective nodal irradiation will NOT be performed for either SBRT or HIGRT, a CTV will NOT be defined.

Treatment Technique:

- **HIGRT:** 3D conformal radiation therapy (3DCRT), static IMRT, or volumetric arc therapy (VMAT) are all permissible techniques for HIGRT. Flattening Filter Free (FFF) treatment is allowed.

- **SBRT:** Due to the close proximity of OARs (especially GI luminal structures) to the PTV and TVI, static IMRT or VMAT must be used; 3DCRT is not permissible. It is recommended that 6-12 co-planar static IMRT fields or 1-3 arc fields (VMAT/Rapid-Arc) be used in the radiation treatment plan. Flattening Filter Free (FFF) treatment is allowed. CyberKnife is a permissible technique for treatment delivery but must be credentialed individually. See [Section 15.1.2](#) for credentialing instructions
- **HIGRT and SBRT:** HIGRT and SBRT treatment plans will be developed using commercially available systems based on tumor geometry and location. Institutional standards for radiation quality assurance and radiation delivery will be utilized (see [Section 6.3](#) for protocol-specific Quality Assurance Documentation).

Motion Management:

- Motion management using respiratory gating or breath-hold (active breathing control), (Varian, Elekta, Novalis), respiratory tracking (CyberKnife), or abdominal compression can reduce cranial-caudal fiducial marker motion from typically 11-22 mm peak to ≤ 5 mm.
- Use of respiratory gating, ABC, or respiratory tracking requires real time cone beam CT, fluoroscopy, or KV imaging to confirm fiducial location during treatment.
- If tumor/fiducial marker motion is > 5 mm despite the use of abdominal compression and/or other motion management techniques listed above are not available, then patients should receive HIGRT instead of SBRT (see [Section 7.2.1](#)).

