13.3 Power Justification

The primary aim of this randomized phase II study is to evaluate 18-month OS rate in patients with borderline resectable cancer of the head of the pancreas treated neoadjuvantly using one of the following regimens: 1) Arm 1: 8 cycles of systemic FOLFIRINOX or 2) Arm 2: 7 cycles - of systemic FOLFIRINOX followed by short-course hypofractionated radiation therapy. All patients who are able to undergo subsequent surgery will also receive 4 cycles of postoperative FOLFOX. Eligible patients will be randomized and stratified by ECOG performance score onto two arms. Within each arm, single-arm sequential design with one interim analysis for futility will be implemented. The final efficacy analysis and interim analysis will be based on 18-month OS rate and R0 resection rate, respectively, and evaluated in each arm separately. The comparison of OS between arms will be carried out only if both arms are deemed promising at the end of the trial. “Pick-a-winner” strategy will be implemented to choose one treatment strategy for recommendation.

An extensive literature review was conducted to evaluate median OS and R0 resection rate in patients purported to have “borderline resectable” tumors who received chemo, chemoRT, etc. were conducted. Twenty-six studies published between 2004 and 2015 are identified with number of borderline resectable patients range from 8 to 129. All but three of these studies are retrospective studies.

The following table summarizes the historical data of median OS and R0 resection rate among all patients started treatment, including both patients with and without surgery.

Time era	Among Studies with N > 20				Among Studies with N > 50			
	N of studies	Weighted	Median	Range (IQR)	N of studies	Weighted	Median	Range (IQR)
Median OS in months								
Prior to 2012	6	21.3	21.5	14.2 – 25 (18.0 – 22.8)	3	22.0	22.0	14.2 – 25 (21.5 – 22.5)
2012 and later	9	21.2	19.9	17.2 – 28 (18.0 – 23.6)	6	21.2	21.0	17.2 – 28 (17.9 – 23.2)
All studies	15	21.2	21.0	14.2 – 28 (17.6 – 23.3)	9	21.5	22.0	15 – 28 (19.0 – 23.0)
R0 Resection Rate Among All Patients Started Neoadjuvant Treatment								
Prior to 2012	6	41.4%	36.9%	30 – 59%	3	43.0%	38.8%	30 – 59%
2012 and later	9	61.2%	54.4%	42 – 92%	6	60.0%	54.2%	42 – 92%
All studies	15	53.0%	53.4%	30 – 92%	9	52.8%	53.9%	37 – 92%

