15.1.2 Radiation Therapy Requirements

Note: Arm 2 closed to new patient enrollment on 08/13/2018. As of Update #04, RT Credentialing is no longer required.

Institutions that have been previously credentialed for participation in RTOG 1112 need only update their Facility Questionnaire as indicated in the table below. All other institutions must be credentialed for the modality they plan to use prior to delivery of radiation therapy on any protocol patient. Credentialing requirements are listed in the table below. Use of IMRT is required for those treating with SBRT. Use of proton therapy is not allowed.

Web Link for Credentialing Procedures and Instructions:
<http://irochouston.mdanderson.org>

	Treatment Modality		
RT Credentialing Requirements	HIGRT	SBRT	Key Information
Facility Questionnaire	X	X	The IROC Houston electronic facility questionnaire (FQ) should be completed or updated with the most recent information about your institution. To access this FQ, email [REDACTED] to receive your FQ link.
Phantom Irradiation		X	An IMRT liver phantom w/motion management study provided by the IROC Houston QA Center must be successfully completed. Instructions for requesting and irradiating the phantom may be found on the IROC Houston website [REDACTED]. Tomotherapy and CyberKnife treatment delivery modalities must be credentialed individually.
	w/IMRT		Successful completion of a phantom study is required. Prior irradiation of the head and neck phantom will be accepted.
IGRT		X	Instructions for IGRT credentialing may be found on the IROC Houston website (http://irochouston.mdanderson.org).
Credentialing Status Inquiry Form	X	X	To determine if your institution has completed the requirements above, please complete a "Credentialing Status Inquiry Form" found under Credentialing on the IROC Houston QA Center website: [REDACTED]
Institution			Institutions will be credentialed for the treatment modality that they intend to use on all patients. Institutions credentialed for use of SBRT may treat with either SBRT or HIGRT. IROC Houston QA Center will notify the institution and Alliance Headquarters that all desired credentialing requirements have been met.

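### The HIGRT versus SBRT survival comparison in Section 13.4.3 is confounded by the protocol's own rules for choosing the technique, so it should be descriptive only

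*Combined protocol and SAP*

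**What the plan says.** The whole analysis is one sentence in Section 13.4.3: "Subgroup analysis will be performed by radiation type (HIGRT vs. SBRT) to examine potential differential effect on overall survival (OS". It names no population, time origin, test, covariates or limit on interpretation.

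Randomization concerns the arm only: "Eligible patients will be randomized and stratified by ECOG performance score onto two arms" (Section 13.3; Section 4.7 lists the same single factor).

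Technique is chosen by rule and by site:

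- **Site or patient suitability.** Section 1.4.7: "if centers are not able to deliver SBRT or the patient is inappropriate for SBRT, then HIGRT will be delivered". Section 7.2: "Centers that are not credentialed for SBRT may treat with HIGRT if appropriately credentialed". Section 15.1.2 adds: "Institutions credentialed for use of SBRT may treat with either SBRT or HIGRT".
- **Invasion.** Section 7.2: "Patients with direct tumor invasion of the bowel or stomach based on endoscopy are not acceptable for SBRT, but may be considered for HIGRT".
- **Organ constraints and dose goals.** Sections 7.2, 7.2.1.1 and 7.2.2.1 direct patients to HIGRT when SBRT constraints or target goals cannot be met within the allowed variation.
- **Motion.** Section 7.2.1.1, on motion that stays above 5 mm: "then patients should receive HIGRT instead of SBRT".
- **Fiducials and insurance.** Section 7.2.1 allows HIGRT when markers cannot be placed. Section 7.2.1.1 restricts patients whose insurance does not cover placement to HIGRT.

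The Study Calendar (Section 5.0, footnote B) puts marker placement and simulation in cycle 5 or 6. Section 7.0 records that Arm 2 closed, and its treatment stopped, on 08/13/2018.

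**The concern.** A subgroup analysis normally compares randomized arms within levels of a baseline characteristic. Radiation type is not such a characteristic. Arm 1 patients, and Arm 2 patients who never reached radiation, have no value for it. Among those who do, the groups differ by design: SBRT patients were judged suitable at a capable site, while HIGRT patients combine those judged unsuitable with those treated where SBRT was unavailable. This is confounding by indication.

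Section 1.4.7 says it is unclear which technique is better before surgery, so readers are likely to look to this result for guidance. An unqualified OS contrast could be read as evidence for one technique when it reflects who was given it.

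**Working it through.** **1. What the plan quantifies.** Section 13.4.3 gives no sample size, power or significance level, so there is no figure of its own to reproduce. The benchmark used below is the 18-month OS of 63% in Section 13.3, and it does reproduce: under exponential survival with median 27 months, S0 = 0.5^(18/27) = 0.630.

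**2. When the technique becomes known.** At a center without SBRT, technique is known in advance. Invasion, insurance and fiducial feasibility might also be known early, since Section 7.2.1 lets markers be placed before enrollment. Constraint failure, dose-goal failure and motion are established at simulation and planning, normally cycle 5 or 6 or later, and so after randomization.

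**3. Spurious gap with identical techniques (assumed values).** Let a feature with hazard ratio h for death be present in a fraction f of HIGRT patients and in no SBRT patients. Then:

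- SBRT 18-month OS = S0 = 0.630
- HIGRT 18-month OS = f × S0^h + (1 − f) × S0
- Gap = f × (S0 − S0^h)

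S0^1.5 = 0.500, S0^2 = 0.397 and S0^3 = 0.250. With f = 0.5:

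| h | HIGRT OS | Gap (points) |
|---|---|---|
| 1 | 63.0% | 0 |
| 1.5 | 56.5% | 6.5 |
| 2 | 51.3% | 11.7 |
| 3 | 44.0% | 19.0 |

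With f = 0.25, the gaps at h = 1.5, 2 and 3 are 3.2, 5.8 and 9.5 points. With f = 0.75 they are 9.7, 17.5 and 28.5. If 10% of SBRT patients also carry the feature and f = 0.5, they are 5.2, 9.3 and 15.2.

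**4. Effect on an unadjusted log-rank test (simulation, assumed values).** There were 4,000 trials per scenario, 62 irradiated patients, no technique effect, and the feature in 30% of patients. HIGRT was given to 90% of those with the feature and 20% of those without. At h = 1, 1.5, 2 and 3 the two-sided 5% test rejected in 5%, 13%, 27% and 54% of trials, and the mean HIGRT:SBRT hazard ratio was 1.00, 1.30, 1.58 and 2.05. Stratifying on the feature brought rejection back to 5–6%. That works only if the feature is recorded and occurs under both techniques. Where invasion bars SBRT, that stratum has no SBRT patients and contributes nothing.

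**5. Precision.** The 95% half-width for the 18-month difference is 1.96 × √[0.63 × 0.37 × (1/nH + 1/nS)]:

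- 62 irradiated: 24 points if split equally, 28 points if a quarter receive HIGRT.
- 30 irradiated: 35 and 40 points.

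The figure of 62 is the planned maximum of evaluable patients per arm (Section 13.2), so it is generous. The number actually irradiated is not given.

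**The case against.** The strongest reply is that this is one exploratory sentence. It is tied to no decision rule in Sections 13.4.1.1 to 13.4.1.3, and it concerns an arm that has closed. Several routing factors (credentialing, insurance, marker feasibility, respiratory motion) need not track tumor severity, and if none is prognostic the spurious gap is zero. This stands as a limit on importance and on certainty. It does not make the comparison interpretable, because the plan has no means of showing that the factors are harmless.

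Four stronger readings are tempting, and the documents do not support them.

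- **That a difference would necessarily appear.** This requires a prognostic routing factor, and the documents give no such estimate.
- **That the gap is about 15 points.** Giving HIGRT patients a median of 14.2 months and SBRT patients 22 yields 18-month OS of 41.5% and 56.7%. But 14.2 is the lowest study-level median in the Section 13.3 table. It reflects variation between studies, not the features that lead to HIGRT.
- **That irradiated patients gain guaranteed survival time over Arm 1.** Section 13.4.3 sets HIGRT against SBRT, and both groups had to survive to radiation. A comparison of either with Arm 1 is not stated.
- **That subgrouping by site credential would rescue the analysis.** Sections 4.2.2 and 15.1.2 required credentialing before radiation delivery, not before enrollment, and the requirement was later dropped. Credential status can therefore depend on the arm assigned, and Arm 1 patients have no treating radiation site.

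**Conclusion.** The concern holds in a limited form. Followed as written, Section 13.4.3 gives a non-randomized comparison confounded by the rules that select the technique. An OS difference could arise between equivalent techniques and could not be attributed to technique. Adjustment cannot repair the comparison where a feature excludes SBRT.

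In the base illustration the spurious gap runs from 0 to 19 points. That rests on exponential survival, a 63% benchmark, and assumed values for feature prevalence and hazard ratio. The direction also depends on the routing features being adverse. Random error of 24 to 40 points either way would in any case leave the comparison weak.

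The primary endpoint analysis is untouched. The change is worth making because the sentence stands unqualified, but it is a should-fix rather than a threat to the trial's main conclusion.

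**What to change.** Replace Section 13.4.3 with a descriptive summary:

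- **Population:** Arm 2 patients who started radiation, grouped by technique received.
- **Time origin:** start of radiation.
- **Content:** Kaplan-Meier estimates with confidence intervals for each technique, plus a table of reasons for HIGRT (site not SBRT-credentialed; invasion; constraints or dose goals; motion; fiducials or insurance).
- **Limits:** no hypothesis test and no claim of a differential effect of technique. State that technique was not randomized, and that Arm 2 closed and its treatment stopped on 08/13/2018.

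Do not substitute a subgroup by site credential.

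The cost is mainly SAP wording. Plans, dosimetry and motion forms were already required under Section 6.3.1, but none of the listed items records why HIGRT was chosen, so some reasons (insurance, for example) may need a site query. The trial gives up a formal comparison of techniques, which the available data could not support.

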13.5 Safety Monitoring

The stopping rule specified below is based on the knowledge available at study development. We note that the Adverse Event Stopping Rule may be adjusted in the event of either (1) the study re-opening to accrual or (2) at any time during the conduct of the trial and in consideration of newly acquired information regarding the adverse event profile of the treatment(s) under

investigation. The study team may choose to suspend accrual because of unexpected adverse event profiles that have not crossed the specified rule below.

Accrual will be temporarily suspended to this study if at any time in either arm we observe the following:

- The rate of on-study deaths during treatment, or within the first 90 days following off-protocol treatment, exceeds 2 or more in the first 10 patients or, after 10 patients enrolled, 20% or more of all treated patients. The rate will be assessed for each arm separately.

Accrual will also be temporarily suspended to this study if prior to surgery we observe events considered at least possibly related to study treatment (i.e. an adverse event with attribute specified as “possible”, “probable”, or “definite”) in each treatment arm, separately, that satisfy the following:

- If 4 or more patients in the first 20 treated patients (or 20% of all patients after 20 are accrued) experience a grade 4 or higher non-hematologic adverse event.

The principal investigator and the study statistician will review the study at least twice a year to identify accrual, adverse event/safety, and any endpoint problems that might be developing. The Alliance Data Safety Monitoring Board (DSMB) is responsible for reviewing accrual and safety data for this trial at least twice a year, based on reports provided by the study statisticians.

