
The CTSU website is located at https://www.ctsuo.org.
		

PREOPERATIVE EXTENDED CHEMOTHERAPY VS. CHEMOTHERAPY PLUS HYPOFRACTIONATED RADIATION THERAPY FOR BORDERLINE RESECTABLE ADENOCARCINOMA OF THE HEAD OF THE PANCREAS

Pre-Registration Eligibility Criteria (see [Section 3.2.1](#))

Cytologic or histologic proof of adenocarcinoma of the pancreatic head or uncinate process.
 TNM Stage: T1-4N0-1orNxM0
 Local radiographic reading consistent with borderline resectable cancer of the pancreatic head

[figure not shown]
Registration Eligibility Criteria (see [Section 3.3](#))

Confirmation of radiographic stage as borderline resectable by central radiographic review
 No prior chemotherapy or radiation for pancreatic cancer and no definitive resection of pancreatic cancer
 No strong CYP3A4 inhibitors or inducers (See [Section 3.3.3](#))
 No grade ≥ 2 neuropathy
 No known Gilbert’s Syndrome or known homozygosity for UGAT1A1*28 polymorphism.
 No uncontrolled gastric ulcer disease (Grade 3 gastric ulcer disease) within 28 days of registration
 Not pregnant and not nursing, because this study involves an agent that has known genotoxic, mutagenic and teratogenic effects.
 Age ≥ 18 years
 ECOG Performance Status 0 or 1

Required Initial Laboratory Values	
Absolute neutrophil count (ANC)	≥ 1500/mm ³
Platelet Count	≥ 100,000/mm ³
Creatinine	≤ 1.5 x upper limit of normal (ULN)
Calc. Creatinine or Clearance (see Alliance website)	> 45 mL/min
Total Bilirubin	≤ 2.0 x mg/dL
AST / ALT	≤ 2.5 x ULN

Schema

As of 08/13/2018, patients will no longer be registered/randomized to Arm 2.

* RT simulation and EUS/ fiducial marker placement is performed during cycle 5 or 6 of mFOLFIRINOX

Surgery and imaging must be conducted at the registering institution. Radiation therapy must be performed at a facility participating in the IROC monitoring program. Chemotherapy may be given at a non-registering institution. If the NCTN Group credited for enrollment is a non-Alliance Group, then other requirements from the credited Group may apply. All protocol conduct must be followed and the registering institution is responsible for ensuring all data is reported per protocol.

Treatment is to continue until disease progression or unacceptable adverse event. Patients will be followed for 5 years or until death, whichever comes first.

Please refer to the full protocol text for a complete description of the eligibility criteria ([Section 3.0](#)) and treatment plan ([Section 7.0](#)).

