After the first set of restaging scans, patients who do not show progression on the local read per [Section 12.1.3](#) will be treated as follows: patients on Arm 1 will receive 4 additional cycles of mFOLFIRINOX, and patients on Arm 2 will receive 3 additional cycles of mFOLFIRINOX and then hypofractionated radiotherapy per [Section 7.2](#). These additional cycles of mFOLFIRINOX for both Arm 1 and Arm 2 should start within 14 days after cycle 4 day 1 unless dose modifications indicate delay.

After preoperative therapy is completed, patients will be restaged, and, if still considered a surgical candidate for resection per the criteria of [Section 3.2.1](#) after central review, will proceed to surgery per [Section 7.3](#). Surgery must occur 4 to 8 weeks after last dose chemotherapy (Arm 1) or of radiation (Arm 2).

Patients considered inappropriate for surgery will go off of study treatment, and are to be followed per the follow-up schedule provided in the study calendar ([Section 5.0](#)).

Following surgery, patients will receive post-operative chemotherapy with 4 cycles of FOLFOX starting 4 to 12 weeks from date of surgery.

Treatment will continue until disease progression or unacceptable adverse event or inability to tolerate treatment even with all allowed dose reductions, or completion of the full treatment program and entrance onto clinical follow-up. Also, see Sections [12.1.3](#) and [12.3](#) for additional information regarding discontinuation of treatment.

See [Section 8.1](#) for ancillary/concomitant therapy guidelines.

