- Grade 1-3 dehydration and hospitalization resulting from such does not require AERS reporting, but should be reported via routine AE reporting
- Grade 3 dehydration does not require AERS reporting, but should be reported via routine AE reporting
- Grade 1-3 fatigue and hospitalization resulting from such does not require AERS reporting, but should be reported via routine AE reporting.
- Grade 3 or 4 fatigue does not require AERS reporting, but should be reported via routine AE reporting
- Grade 1-4 hematosuppression (leukopenia, neutropenia, lymphopenia, anemia, and thrombocytopenia) with hospitalization resulting from such

do not require AERs reporting, but should be reported via routine AE reporting

- Grade 3 or 4 hematosuppression (leukopenia, neutropenia, lymphopenia, anemia, and thrombocytopenia) does not require AERs reporting, but should be reported via routine AE reporting
- Deaths that occur within 90 days of surgery required CTEP-AERS reporting regardless of attribution, including in the case of progressive disease.
- Death due to progressive disease should be reported as Grade 5 “Disease progression” in the system organ class (SOC) “General disorders and administration site conditions.” Evidence that the death was a manifestation of underlying disease (e.g. radiological changes suggesting tumor growth or progression: clinical deterioration associated with disease process) should be submitted.
- Any death occurring within 30 days of the last dose, regardless of attribution to the investigational agent/intervention requires expedited reporting within 24 hours.
- Any death occurring greater than 30 days after the last dose of the investigational agent/intervention requires expedited reporting within 24 hours only if it is possibly, probably, or definitely related to the investigational agent/intervention.
- Pregnancy loss
 - Pregnancy loss is defined in CTCAE as “Death in utero.”
 - Any Pregnancy loss should be reported expeditiously, as Grade 4 “Pregnancy loss” under the Pregnancy, puerperium and perinatal conditions SOC.
 - A Pregnancy loss should not be reported as a Grade 5 event under the Pregnancy, puerperium and perinatal conditions SOC, as currently CTEP-AERS recognizes this event as a patient death.
- A neonatal death should be reported expeditiously as Grade 4, “Death neonatal” under the General disorders and administration SOC.

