13.2 Sample Size

We anticipate enrolling a maximum of 124 evaluable patients (62 per arm) per statistical design. Additional 10 (5 per arm) patients will be accrued to account for cancelations, ineligibilities, major violations, and lost-to-follow up, etc. Thus the total targeted accrual will be 134 patients.

We anticipate to pre-register 5 patients per month. Since we estimate 80% of patients who are pre-registered for central review will be randomized to therapy, the actual accrual will be 4 patients per month. Thus, we expect to pre-register 168 patients to reach the targeted accrual of 134 patients. The accrual period of this study is estimated to be 34 months.

We also expect that 40% of patients randomized to therapy will be off protocol treatment prior to surgery (i.e. will not undergo surgery). Therefore we expect that of the 134 patients, 80 will proceed to surgery. The primary endpoint, overall survival at 18 month post randomization, is well-defined even among patients who do not receive surgery. Therefore, the percentages of patients who do not undergo surgery do not affect the trial design.

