We consider studies with reasonable number of borderline resectable patients (e.g. N > 20, and/or N > 50) to estimate the historical estimates of the median OS and R0 resection rate for sample size and power determinations. There is substantial variability in the literature reported median OS across studies. The median OS reported in these studies varies from 14 to 28 months, with a median of 21 to 22 months and an interquartile range of about 18 to 23 months. Most of the previous studies are retrospective single-institution studies subject to patient selection bias, which likely to skew the reported OS higher. Thus, we consider the median OS of at most 18 months (equivalent to 18m OS rate of 0.50, assuming exponential survival function) which is the lower bound of the IQR of literature reported data as the null hypothesis. To demonstrate clinical meaningful improvement in OS, we target an alternative hypothesis of median OS of at least 27 months (equivalent to 18m OS rate of 0.63; a 50% increase in median OS time).

The summary data in the table shows clear increase trend of R0 resection rate over time. For interim analysis based on R0 resection rate, if R0 resection rate is at least 60% (null hypothesis) based on weighted R0 resection rate from historical data, the arm warrants continuing to full accrual for OS final analysis. If the observed R0 resection rate is significantly less than 60%, we consider early futility of the arm and stop accrual of patients onto that arm. Therefore, the interim analysis based on R0 resection rate will be testing alternative hypothesis of R0 resection rate $\leq 40\%$ against the null hypothesis of R0 resection rate $\geq 60\%$.

The study operating characteristics were assessed by simulation studies based on the estimation procedures and decision rules specified for final and interim analysis described in [Section 13.4.1](#). A maximum of 62 evaluable patients in each arm will provide 82% power to detect an improvement of 13% in 18 months OS rate, i.e., testing alternative hypothesis that the 18 months OS rate is at least 63% against the null hypothesis that the 18 months OS rate is at most 50%, at a one-sided significance level of 0.07. The probability of stopping accrual at interim is 43% and 0.8% if the true R0 resection rate is 40% and 60%, respectively.

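### Does the death rule in section 13.5 need a new boundary because expected disease deaths alone could trip it?

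*Combined protocol and SAP*

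**What the plan says.** Section 13.5 has two suspension rules, each applied to the arms separately. The death rule is met when the number of "on-study deaths during treatment, or within the first 90 days following off-protocol treatment, exceeds 2 or more in the first 10 patients". A second limb then takes over, worded as follows: "after 10 patients enrolled, 20% or more of all treated patients". It carries no attribution limit. The second rule covers grade 4 or higher non-hematologic events before surgery that are at least possibly related to treatment; its limit is 4 or more of the first 20 treated patients, then 20%. Crossing either limit suspends accrual temporarily. The section lets the adverse event stopping rule be adjusted during the trial as information accrues, and the DSMB reviews safety at least twice a year.

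The window is long. Under sections 7.0 and 7.1, Arm 1 receives 8 cycles of 14 days, has surgery 4 to 8 weeks after the last chemotherapy dose, and then receives "4 cycles of FOLFOX starting 4 to 12 weeks from date of surgery". Section 13.2 expects that "40% of patients randomized to therapy will be off protocol treatment prior to surgery". Section 13.3 assumes exponential survival, with a median of 18 months under the null and 27 months at the target. Arm 2 is closed: "As of 08/13/2018, patients will no longer be registered/randomized to Arm 2".

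**The concern.** Three things look wrong at first sight.

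- The death rule counts disease deaths over most of the first year in a lethal cancer, so a 20% limit may sit at the mortality of a regimen that is meeting its survival goal.
- Section 13.3 states stopping probabilities for the R0 futility look (43% and 0.8%), but nothing comparable is given for the death rule.
- Exceeding a limit of 2 or more can be read as at least 2 or at least 3 deaths, and the text does not say outright that the first-10 limb lapses once more than 10 patients are enrolled.

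At stake would be avoidable pauses in the only open arm, a signal that does not separate toxicity from disease, and two readers acting differently on the same count.

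**Working it through.** **Plan's own figures.** With S(t) = 2^(−t/median), S(18) = 2^(−18/27) = 0.63 at the target and 2^(−18/18) = 0.50 at the null, as section 13.3 states.

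**Window length.** Completers are on treatment for 16 + 4 + 4 + 8 = 32 weeks at the shortest and 16 + 8 + 12 + 8 = 44 weeks at the longest. The plan does not say when the 40% who miss surgery come off treatment. I take week 8 (first restaging), week 16 (end of chemotherapy) or week 24 (end of the surgical window). Dating from day 1 of the last cycle shortens each part. Each window then adds 90 days.

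**Expected deaths in the window.** p = 0.4 × [1 − S(a + 90 d)] + 0.6 × [1 − S(b + 90 d)], where a is weeks to exit without surgery and b is weeks for completers. For (16, 32), the windows are (16×7+90)/30.44 = 6.64 months and (32×7+90)/30.44 = 10.32 months. At median 27 the death probabilities are 0.157 and 0.233, so p is about 0.20.

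| Exit week, completion week | Median 27 | Median 18 |
|---|---|---|
| 16, 32 | 0.202 | 0.287 |
| 24, 44 | 0.249 | 0.349 |
| 14, 28 (last-dose dating) | 0.187 | 0.267 |
| 22, 40 (last-dose dating) | 0.235 | 0.331 |
| 8, 28 | 0.175 | 0.250 |
| 8, 44 | 0.217 | 0.305 |

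On the plan's model, then, 20% lies inside the range expected at the target. If the early hazard is lower (an assumed Weibull shape of 1.5, still with 63% alive at 18 months), the range is 12% to 20.5%, almost all of it below the limit.

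**Chance of a pause.** I simulated one arm of 62 patients at the target, checking at each death during accrual, with treated patients to date as the denominator. The first-10 limb was read as at least 2 deaths, ending once 10 are enrolled. The ranges run over schedules from (8, 28) to (24, 44).

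| Scenario | Probability of a pause |
|---|---|
| Exponential, 2 patients per month | 0.46 to 0.76 |
| Exponential, 4 per month into Arm 1 | 0.20 to 0.36 |
| Weibull shape 1.5, 2 per month | 0.12 to 0.41 |

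If the first-10 cohort is instead watched throughout accrual, the first row becomes 0.62 to 0.87.

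**First-10 wording.** At a 20% death rate, P(at least 2 of 10) = 1 − 0.8^10 − 10 × 0.2 × 0.8^9 = 0.62, and P(at least 3 of 10) = 0.32. The reading therefore matters, but the context points one way. The same sentence continues with a limit of 20% or more, and 2/10 = 20%. The companion rule is built alike, with 4 or more of 20, and 4/20 = 20%. The phrase introducing the second limb reads most naturally as a switch from one limb to the other.

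**What a higher limit would do.** At 62 treated patients, 20% is 12.4, so 13 deaths cross it. A limit at the top of the expected range, 25%, is 15.5, so 16 deaths would be needed. This only illustrates the trade and proposes no limit.

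**The case for a change.** The strongest case for a change is that the count cannot tell disease from harm. Adding 10% toxic deaths over the first 6 months to an on-target arm gives a trigger probability of 0.86 to 0.97. An arm at the null median with no toxic deaths gives about 0.85 to 0.98. The two are indistinguishable by count, constant hazard is the plan's own assumption, and a short simulation would have shown all this in advance.

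The arithmetic stands. The inference that the limit must move does not. The rule opens a review and does not assign cause. Section 9.4 requires routine and expedited reporting of on-study deaths whatever the cause, asks for attribution, and has deaths from progression reported as such with supporting evidence. It adds: "Deaths that occur within 90 days of surgery required CTEP-AERS reporting regardless of attribution". For deaths more than 30 days after the last dose, its separate 24-hour requirement applies only to those at least possibly related, which itself calls for an attribution judgement. Whoever reviews a pause would therefore have causes of death to look at.

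The size also depends heavily on assumptions. The upper figures keep every non-surgical patient on treatment to week 24 and assume that every surgical patient completes FOLFOX. Yet section 12.1.3 removes patients for metastatic disease, aborted operations and R2 resections, and the first restaging comes after 4 cycles. Earlier removals shorten the window and lower the rates.

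**Conclusion.** No change to the plan is called for. Under constant hazard at the 27-month target, about 17.5% to 25% of patients would die in the window, and an on-target Arm 1 has roughly an even to three-in-four chance of a temporary pause at 2 patients per month. With a lower early hazard or 4 patients per month into Arm 1, the chance is about 0.12 to 0.41. These figures rest on assumed exit times for the 40% without surgery and on full FOLFOX completion.

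A cautious all-cause limit that only pauses accrual, in a rule the team may adjust, is a fair trade-off. Raising it would mean fewer pauses but more deaths before automatic review, and that judgement belongs to the sponsor and the DSMB. The missing expected rate and trigger probability are background that the study statistician can supply when a review is held; they alter neither the OS test nor the R0 look. The first-10 phrase is a drafting slip, sensibly read as at least 2 of 10 and then 20% once more than 10 are enrolled.
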